Study Objectives	
Primary Safety Objectives:
 
 • Determine if apixaban is superior to warfarin in the reduction of clinically relevant bleeding. • Determine if rivaroxaban is superior to warfarin in the reduction of clinically relevant bleeding 
Primary Efficacy Objectives:
 
 • Determine if apixaban is non-inferior to warfarin in the prevention of recurrent venous thromboembolism. • Determine if rivaroxaban is non-inferior to warfarin in the prevention of recurrent venous thromboembolism. 
Exploratory Objective:
 
 • An exploratory descriptive comparison of apixaban versus rivaroxaban for the prevention of clinically relevant bleeding and recurrent VTEs as a secondary objective.
Study Design	Randomized, open label, active comparator
Treatment Regimen	Warfarin, apixaban, or rivaroxaban
Duration of Study Participation	12 months
Number of Patients	Approximately 3000
Number of Sites	Approximately 60 sites in the US and Canada
Primary Efficacy Endpoint	Recurrent venous thromboembolism
Primary Safety Endpoint	Clinically relevant bleeding
Interim Analyses	There will be no formal interim analyses for the primary efficacy or safety endpoints. The Data and Safety Monitoring Board will meet regularly to review patient safety and overall study conduct.

TABLE OF CONTENTS

Protocol Version and Amendment Tracking	3
Protocol Synopsis.....	4
Table of Contents.....	5
Abbreviations.....	7
1. Introduction.....	9
1.1 Background.....	9
1.2 Preclinical Findings	9
1.3 Long-term prevention of recurrent VTE (after treatment of acute event) .	10
1.4 Clinical Experience with Study Agents	11
1.5 Rationale for COVET	12
2. Objectives and Endpoints	13
2.1 Primary Safety Objectives	13
2.2 Primary Efficacy Objectives.....	13
2.3 Secondary Objectives.....	13
2.4 Primary Safety Endpoint.....	13
2.5 Primary Efficacy Endpoint	13
2.6 Other Study Endpoints.....	13
3. Patient Selection.....	15
3.1 Inclusion Criteria	15
3.2 Exclusion Criteria	15
4. Study Design.....	18
4.1 Overview of Study	18
4.2 Treatment Arms	18
4.3 Study Procedures	20
4.4 Schedule of Follow-Up Assessments.....	22
4.5 Screening and Pre-randomization Procedures	23
4.6 Randomization	23
4.7 Post-randomization Procedures	24
5. Treatment Arms	25
5.1 Study Drug Administration.....	25
5.2 Potential Benefits/Risks of Study Medications.....	25
5.3 Procedure to Assess Medication Adherence.....	25

RR	Relative Risk
SAC	Study Advisory Committee
VTE	Venous Thromboembolism
VKA	Vitamin K Antagonists

V/Q	Ventilation Perfusion
-----	-----------------------

1. INTRODUCTION

1.1 Background

Venous thromboembolism (VTE), including deep vein thrombosis (DVT) and pulmonary embolism (PE), is a common, potentially fatal, yet treatable condition and is the third leading cause of mortality by cardiovascular disease (White 2003; Heit 2006; Kyrle 2004). It represents an important health care issue due to its high rate of hospital admission and potential reduction in functional status of survivors due to VTE related complications such as post-thrombotic syndrome and chronic thromboembolic pulmonary hypertension. Up to 5% of the population will experience VTE in their lifetime and the majority of these events will be unprovoked (White 2003). VTE is predominantly a disease of the elderly with incidence rates increasing exponentially with age for both men and women (White 2003; Heit 2006; Kyrle 2004). The standard therapy for patients with VTE is anticoagulation for 3-6 months; the most common oral anticoagulants used are vitamin K antagonists (VKA) and direct oral anticoagulants (DOACs) (Kearon 2012).

After completing 3-12 months of anticoagulation, patients, clinicians and policy makers are faced with the crucial decision of whether or not to continue anticoagulation lifelong. In patients with unprovoked VTE, the risk of recurrent VTE is substantial, reaching 5%-10.8% in the first year after stopping 3-6 months of VKA, 5% in the subsequent year (Agnelli 2001) and 2-3% per year thereafter (Agnelli 2001; Prandoni 1996; Kearon 1999; Schulman 1995; Research Committee 1992), with a case-fatality rate for recurrent VTE of 3.6% (Carrier 2010). Since up to 75% of unprovoked VTE patients would benefit from continuing anticoagulants lifelong (Rodger 2008), current guidelines recommend indefinite anticoagulant therapy for patients in this category (Kearon 2016). With this decision, the next crucial question becomes which anticoagulant to choose. Treatment with VKA presents many challenges including drug and food interactions, and a narrow therapeutic window requiring regular laboratory monitoring; these can be particularly burdensome for elderly patients and those with many co-morbidities who require intensive monitoring, frequent trips to the laboratory and subsequent dosing changes. DOACs are simpler to use as they have more predictable pharmacokinetic properties (Vilchez 2014) and do not require monitoring. A major limitation of DOACs however, is the lack of comparison trials demonstrating a favorable benefit-to-risk ratio of DOACs over VKAs for long term anticoagulation in VTE patients. This gap in the evidence highlights the decisional dilemma patients, clinicians, and stakeholders are faced with when choosing which anticoagulant to use for long-term prevention of recurrent VTE.

1.2 Preclinical Findings

The information on comparative effectiveness between rivaroxaban or apixaban and warfarin (target INR 2-3) is derived from industry-sponsored trials for treatment of acute VTE (Einstein Investigators 2010; Buller 2012; Agnelli 2013a). The duration of treatment in these trials was defined as the initial 3-12 months of anticoagulation after diagnosis of acute VTE. Einstein-DVT included nearly 3500 patients with proximal DVT and no symptomatic PE (Einstein Investigators 2010). Rivaroxaban was shown to be non-inferior to warfarin for the primary efficacy outcome of recurrent VTE with an event rate of 2.1% in the rivaroxaban arm and 3.0% in the warfarin arm (hazard ratio (HR), 0.68; 95% confidence interval (CI), 0.44 to 1.04). The

primary safety outcome was clinically-relevant bleeding, a composite of major bleeding or clinically-relevant non-major bleeding events, occurred in 8.1% of patients in each group. Einstein-PE enrolled 4800 patients with acute PE with or without DVT (Buller 2012). The primary efficacy and safety outcomes were identical to the Einstein-DVT trial. Rivaroxaban was similarly shown to be non-inferior to warfarin for the primary efficacy outcome with 2.1% of patients in the rivaroxaban arm versus 1.8% in the warfarin having recurrent events (HR 1.12; 95% CI, 0.75 to 1.68). Bleeding occurred in 10.3% of patients in the rivaroxaban group and 11.4% in the warfarin group. The Amplify RCT compared apixaban to warfarin in 5400 patients with acute VTE (Agnelli 2013a). The primary efficacy outcome of recurrent VTE occurred in 2.3% of patients in the apixaban group and 2.7% in the warfarin group (Relative risk (RR), 0.84; 95% CI, 0.60 to 1.18), demonstrating non-inferiority of apixaban to warfarin. The primary safety outcome of major bleeding occurred in 0.6% of patients in the apixaban group compared to 1.8% in the warfarin group, meeting pre-specified criteria for superiority.

1.3 Long-term prevention of recurrent VTE (after treatment of acute event)

Rivaroxaban and apixaban have each been compared to placebo for extended anticoagulation in patients who had completed 6 to 12 months of anticoagulation for the index VTE event (Einstein Investigators 2010; Agnelli 2013b). In both trials, extended anticoagulation treatment was for 12 months duration, the primary efficacy outcome was recurrent VTE and the primary safety outcome was major bleeding. In the Einstein-EXT RCT, 1200 patients were included and rivaroxaban was superior to placebo for preventing recurrent VTE (1.3% for rivaroxaban and 7.1% for placebo; HR, 0.18; 95% CI, 0.09 to 0.39) (cf. Table 1). Major bleeding events occurred in 0.7% of patients in the rivaroxaban group compared to no bleeding events in those on placebo. Clinically relevant bleeding (MB or CRNMB) events occurred in 6.0% of patients receiving rivaroxaban and 1.2% of those on placebo (cf. Table 2). The Amplify-EXT RCT compared two doses of apixaban (5 mg and 2.5 mg, twice daily) to placebo (Agnelli 2013b). Both doses of apixaban were superior to placebo in this trial of 2500 patients. The rates of recurrent VTE were 1.7% in each apixaban group compared to 8.8% in the placebo group (Table 1). Major bleeding events occurred in 0.2% in the 2.5 mg apixaban group, 0.1% in the 5 mg apixaban group, and in 0.5% of the placebo group. Clinically relevant bleeding (MB or CRNMB) events occurred in 3.2% of patients receiving apixaban 2.5 mg and 2.7% of those on placebo (cf. Table 2).

Table 1: Recurrent VTE event rates in Phase III VTE Secondary Prevention Trials

Study	Outcome	Comparator 1	Comparator 2	Hazard Ratio (95% CI)
RE-MEDY	Recurrent VTE or VTE-related death	Dabigatran: 1.2%	Warfarin: 0.87%	1.44 (0.78-2.64)
EINSTEIN-EXT	Recurrent VTE	Rivaroxaban: 1.3%	Placebo: 7.1%	0.18 (0.09-0.39)
AMPLIFY-EXT	Recurrent VTE or VTE-related death	Apixaban 2.5 mg BID: 1.7%	Placebo: 8.8%	Relative Risk: 0.19 (0.11-0.33)
AMPLIFY-EXT	Recurrent VTE or VTE-related death	Apixaban 2.5 mg BID: 1.7%	Apixaban 5 mg BID: 1.7%	Relative Risk: 0.97 (0.46-2.02)

Table 2: Clinically Relevant Bleeding (Major Bleeding [MB] and clinically relevant non-major bleeding [CRNMB]) event rates in Phase III VTE Secondary Prevention Trials

Study	Outcome	Comparator 1	Comparator 2	Hazard Ratio (95% CI)
RE-MEDY	MB or CRNMB	Dabigatran: 5.6%	Warfarin: 10.2%	0.54 (0.41-0.71)
EINSTEIN-EXT	MB or CRNMB	Rivaroxaban: 6.0%	Placebo: 1.2%	5.19 (2.3-11.7)
AMPLIFY-EXT	MB or CRNMB	Apixaban 2.5 mg BID: 3.2%	Placebo: 2.7%	Relative Risk: 1.20 (0.69-2.10)
AMPLIFY-EXT	MB or CRNMB	Apixaban 2.5 mg BID: 3.2%	Apixaban 5 mg BID: 4.3%	Relative Risk: 0.74 (0.46-1.22)

1.4 Clinical Experience with Study Agents

The standard oral anticoagulant that has long been used for extended treatment of VTE has been VKAs. Warfarin is the most common VKA available in North America and it is an effective anticoagulant that reduces the risk of recurrent VTE by >90% (Castellucci 2013). We have set the outcome of our comparative effectiveness study for superiority relative to warfarin. Despite its effectiveness, there are several limitations of warfarin use including the narrow therapeutic window, frequent INR monitoring to ensure patients remain in target range of 2-3, and many food and drugs interactions. The need to monitor INRs can be burdensome for patients and interfere with regular activities and functioning. DOACs have simplified anticoagulation treatment for many patients because they do not require laboratory monitoring for dosing adjustments. There are four DOACs available for treatment of VTE in the United States and Canada – dabigatran, edoxaban, rivaroxaban and apixaban. Edoxaban has not been studied for extended anticoagulation in VTE so we have excluded it from the trial. Dabigatran has been associated with higher rates of acute coronary syndromes in previous VTE trials and we excluded it from our proposed trial (Schulman 2012; Connolly 2009).

The DOACs rivaroxaban and apixaban were chosen as the intervention anticoagulants for the proposed trial. Rivaroxaban and apixaban are two Factor Xa inhibitors that are at least as effective and safe as warfarin for treatment of acute VTE (Einstein Investigators 2010; Buller 2012; Agnelli 2013a). Each DOAC has also been compared to placebo for extended anticoagulation in patients with VTE, demonstrating significantly lower rates of recurrent VTE and similar or lower rates of major bleeding events (Einstein Investigators 2010; Agnelli 2013b). The differences between the medications are in their dosing frequency as rivaroxaban is once daily and apixaban is twice daily. Both medications are currently approved by the FDA and Health Canada and are widely available from commercial pharmacies. Direct comparison of these anticoagulants to warfarin will enable us to determine whether they are as efficacious and as safe as warfarin for extended VTE treatment.

1.5 Rationale for COVET

Vitamin K antagonists were the only oral anticoagulants available for many years and DOACs have expanded the choices now available. Although the Einstein and Amplify trials have changed clinical practice management for patients with acute VTE, generalizability of their results for extended anticoagulation are limited for the following reasons: a) treatment duration was shorter than what would be expected for extended anticoagulation; b) the trials contained patients with both provoked and unprovoked VTE; c) the patients were highly selected from populations that do not reflect clinical practice; d) lack of head-to-head comparisons of DOACs. Only one trial comparing a DOAC (dabigatran) to VKA for extended anticoagulation has been done (Schulman 2012) and no comparative efficacy or safety data exists for rivaroxaban and apixaban relative to warfarin for extended anticoagulation; and e) previous clinical trials were sponsored by industry and there is no interest by the manufacturers to conduct head-to-head comparisons of anticoagulants. Our study will advance knowledge in this field as it is a pragmatic comparison trial that will potentially change practice and resolve the decisional uncertainty patients and clinicians face when choosing an anticoagulant for extended treatment.

2. OBJECTIVES AND ENDPOINTS

2.1 Primary Safety Objectives

In patients at high-risk for recurrent VTE, the COVET trial will

- Determine if apixaban is superior to warfarin, target INR 2-3, in the reduction of clinically relevant bleeding.
- Determine if rivaroxaban is superior to warfarin, target INR 2-3 in the reduction of clinically relevant bleeding.

2.2 Primary Efficacy Objectives

In patients at high-risk for recurrent VTE, the COVET trial will

- Determine if apixaban is non-inferior to warfarin, target INR 2-3, in the prevention of recurrent venous thromboembolism.
- Determine if rivaroxaban is non-inferior to warfarin, target INR 2-3, in the prevention of recurrent venous thromboembolism.

2.3 Secondary Objectives

In patients at high-risk for recurrent VTE, the COVET trial will

- Compare the rates of clinically relevant bleeding between apixaban and rivaroxaban.

2.4 Primary Safety Endpoint

Clinically relevant bleeding (composite of major bleeding (MB) and/or clinically relevant non major bleeding (CRNMB)) is the primary safety outcome which specifically addresses concerns relevant to all patients with VTE. Our criteria to define clinically relevant bleeding are consistent with those in the aforementioned VTE trials and published by the International Society on Thrombosis and Haemostasis (ISTH) (Kaatz 2015).

2.5 Primary Efficacy Endpoint

Recurrent VTE is the primary efficacy outcome, defined according to criteria described in the 2012 Chest Guidelines for Diagnosis of DVT (Bates 2012) and 2014 European Society of Cardiology Guidelines for Diagnosis of PE (Konstaninides 2014). This outcome is patient centered and important for all stakeholders given the clinical (symptoms of pain and discomfort), social, and economic burden associated with it.

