2.6 Other Study Endpoints

- All-cause mortality
- Major bleeding
- Clinically relevant non-major bleeding

- Premature termination of study medication
- Vascular events (myocardial infarction, ischemic stroke)

These study endpoints will be defined in detail in the Clinical Event Classification (CEC) charter.

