6.2 Adverse Events

The COVET study is designed to be a pragmatic trial comparing three therapeutic agents approved by the regulatory agencies in the United States (Food and Drug Administration) and Canada (Health Canada) for the extended treatment of patients with an unprovoked DVT or PE to prevent recurrent thromboembolism. We will be collecting adjudicated outcome events, including bleeding, that have been shown to account for the majority of SAE's based on a large number of patients treated in several clinical studies. These outcome events, listed above in Section 2, include the following:

- Clinically relevant bleeding, which is the composite of major bleeding and/or clinically-relevant, non-major bleeding, as defined by ISTH criteria (Kaatz, 2015)
- Recurrent VTE, as defined above (Section 2.5), representing failure in efficacy
- All-cause mortality
- Vascular events, including myocardial infarction and ischemic stroke

All study endpoints will be identified during scheduled contact with the study participants at 1 month, 6 months, and 12 months (see Table 3) and reported to the P.I., co-P.I.'s, and study leadership at DCRI within 24 hours. All events will then be independently adjudicated by the Clinical Event Classification committee (section 11.9).

Pregnancy is also collected as part of the COVET study (section 6.3) and will be reported within 24 hours as described for the outcome events documented above.

Study drug discontinuation is also collected as part of the COVET study, including the reason for discontinuation of the study drug. Laboratory tests are not being collected in the COVET study.

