7.2 Sample Size Justification

The planning and sample size calculations for the COVET study were designed to compare warfarin vs. apixaban and warfarin vs. rivaroxaban. A direct exploratory and descriptive comparison of the two DOACs will be conducted but the study was not powered to detect statistically significant differences between those treatment groups.

For the primary safety endpoint, there will be two comparisons, apixaban versus warfarin and rivaroxaban versus warfarin, each of which will be tested at the two-sided 0.05 level of significance to detect a 50% reduction (HR=0.50) in clinically relevant bleeding compared to warfarin. For the primary efficacy endpoint, there will be two comparisons, apixaban versus warfarin and rivaroxaban versus warfarin to determine if the DOACs are non-inferior to warfarin in the prevention of recurrent venous thromboembolism. The non-inferiority assessments will be based on comparing the one-sided 95% upper confidence interval with a 2% absolute risk increase for recurrent VTE.

The type I error rates for the non-inferiority and superiority analyses have been set at 0.05 one-sided and 0.05 two-sided, respectively. These are considered standard values for two

arm studies. We have elected to not alter them for this three-arm design because the clinical questions of interest are the two comparisons of the DOACs versus warfarin.

For the primary efficacy analysis, using an outcome of recurrent VTE, we expect 12-month rate of 0.87% for the warfarin arm compared with 1.5% for the DOACs (Einstein Investigators 2010; Agnelli 2013). Sample sizes of 950 per arm are sufficient to provide 80% power to have the upper 95% one-sided confidence interval less than 2%. The proposed sample size of 1000 participants per arm allows for 5% missing data due to loss-to-follow-up, deaths not related to VTE, and lack of starting the assigned study drug. These calculations were obtained using a simulation method with nQuery Advisor 7.0 software.

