7.5 Data Analyses

Baseline characteristics will be presented using mean (standard deviation) and median (25th, 75th percentiles) for continuous variables and as frequencies (percentages) for categorical variables. No formal comparisons will be computed for baseline variables.

The primary analyses for safety primary endpoint will be based on an un-stratified Cox model adjusting for the two treatment indicators and three stratification indicators. The ascertainment time will be based on the time of the first event or censoring time. Stratification will be based on the anticoagulant used during the screening period. The all-randomized (ITT) analysis dataset will be used for the primary analyses. The treatment effect for each DOAC compared to warfarin will be computed using the estimated hazard ratio and associated 95% confidence intervals. Secondary analyses will be based on a Kaplan-Meier estimates on the all-randomized (ITT) and per-protocol populations.

For the efficacy primary endpoint, the primary analysis will be based on a Kaplan-Meier analysis using the all-randomized (ITT) analysis dataset. The 12-month event rates differences between the DOACs versus warfarin will be based on the difference in the Kaplan-Meier estimates and the one-sided upper 95% confidence interval will be based on a bootstrap estimator. Secondary analyses of the recurrent VTE endpoint will be based on the Cox regression model. Exploratory analyses will directly compare the two DOACs for both safety and efficacy endpoints. Additionally, an exploratory analysis will pool the two DOAC arms and compare those estimates with the warfarin treatment group.

For secondary endpoints, the estimated differences between the DOACs and warfarin treated groups will be based on linear models, logistic regression, and Cox models depending on the endpoint. Efforts will be made to limit the amount of missing data for the key endpoints and adherence measures. When necessary, multiple imputation will be used to account for missing covariate information.

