9.3 Analysis of Time to “Response” Data

9.3.1 Primary and Secondary Endpoint Analysis

The primary analyses for safety primary endpoint will be based on a stratified Cox model. The ascertainment time will be based on the time of the first event or censoring time. Stratification will be based on the anticoagulant used during the screening period. The all-randomized analysis dataset will be used for the primary analyses. The treatment effect for each DOAC compared to warfarin will be computed using the estimated hazard ratio and

associated 95% confidence intervals. Secondary analyses will be based on a Kaplan-Meier estimates on the all-randomized and per-protocol populations.

For the efficacy primary endpoint, the primary analysis will be based on a Kaplan-Meier analysis using the all-randomized analysis dataset. The 12-month event rates differences between the DOACs versus warfarin will be based on the difference in the Kaplan-Meier estimates and the one-sided upper 95% confidence interval will be based on a bootstrap estimator. Secondary analyses of the recurrent VTE endpoint will be based on the Cox regression model. Exploratory analyses will directly compare the two DOACs for both safety and efficacy endpoints. Additionally, an exploratory analysis will pool the two DOAC arms and compare those estimates with the warfarin treatment group.

For secondary endpoints, the estimated differences between the DOACs and warfarin treated groups will be based on linear models, logistic regression, and Cox models depending on the endpoint. Efforts will be made to limit the amount of missing data for the key endpoints and adherence measures. When necessary, multiple imputation will be used to account for missing covariate information.

References

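### Does the primary efficacy endpoint need a stated rule for VTE-related deaths, and for other deaths in the Kaplan-Meier analysis?

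*Protocol*

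**What the plan says.** Protocol 2.5 and SAP 6.1.2 use the same definition: "Recurrent VTE is the primary efficacy outcome, defined according to criteria described in the 2012 Chest Guidelines for Diagnosis of DVT", together with a European guideline for diagnosing pulmonary embolism. Death is not mentioned. Protocol 6.2 refers back to that section: "Recurrent VTE, as defined above (Section 2.5), representing failure in efficacy".

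The sample-size text in Protocol 7.2 and SAP 7 says that 1000 per arm "allows for 5% missing data due to loss-to-follow-up, deaths not related to VTE, and lack of starting the assigned study drug". Deaths caused by VTE are not on that list.

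Table 1 in Protocol 1.3 labels the rows that hold the 0.87% warfarin rate and the 1.7% apixaban rate "Recurrent VTE or VTE-related death". The text of the same section says "The rates of recurrent VTE were 1.7% in each apixaban group compared to 8.8% in the placebo group". The 1.3% rivaroxaban rate is labelled as recurrent VTE alone.

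On analysis, Protocol 7.5 says "For the efficacy primary endpoint, the primary analysis will be based on a Kaplan-Meier analysis using the all-randomized (ITT) analysis dataset", and SAP 9.3.1 says "For the efficacy primary endpoint, the primary analysis will be based on a Kaplan-Meier analysis using the all-randomized analysis dataset". Neither adds a rule for participants who die. A censoring time is mentioned only in the safety paragraph of each document and is not defined.

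On adjudication, Protocol 7.1 sends all potential endpoints to a central committee blinded to treatment. Protocol 11.9 gives that committee bleeds, recurrent VTE and deaths, with the guidelines in the CEC Charter. SAP 5 names the committee's database as part of the analysis data source. Protocol 2.6 adds "These study endpoints will be defined in detail in the Clinical Event Classification (CEC) charter", but that sentence stands under the other endpoints, not under recurrent VTE.

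**The concern.** A participant may die suddenly, with the death attributed to pulmonary embolism but no imaging or autopsy. Read literally, the endpoint definition leaves this death out. The sample-size wording suggests that it is in, and the source of the 0.87% planning rate included such deaths. On this view, two analysts could count the same death differently.

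The stakes look high because the efficacy test is a non-inferiority test on an absolute difference with few events. If a similar share of events is dropped from both arms, the difference shrinks in proportion and non-inferiority becomes easier to declare. The missing rule for other deaths in the Kaplan-Meier estimate looks like a second loose end in the same primary analysis.

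**Working it through.** **Inputs.** From Protocol 7.2 and SAP 7: 12-month rates of 0.87% (warfarin) and 1.5% (DOAC), margin m = 2 percentage points (stated as absolute in the protocol), one-sided 0.05 (z = 1.645), n = 950 per arm, stated power 80%. From Protocol 1.1: case fatality of recurrent VTE 3.6%. Assumed: the share q of events that are VTE deaths without a diagnosis, and mortality from other causes.

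**1. The plan's own power.** The Farrington-Manning score formula is Φ{[(m − d)√n − z·s0] / s1}, with d = 0.0150 − 0.0087 = 0.0063. The rates fitted at the margin are 0.607% and 2.607%, so s0 = 0.1773; the planning rates give s1 = 0.1530.

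(0.0137 × 30.82 − 1.645 × 0.1773) / 0.1530 = 0.854, and Φ(0.854) = 80.4%.

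The stated 80% reproduces. The plain unpooled (Wald) formula gives 86.8%, so it is not the method behind the stated figure. The inflation also agrees: 950 / 0.95 = 1000.

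**2. Events at stake.** Expected events are 950 × 0.0087 = 8.3 and 950 × 0.015 = 14.3, about 22.5 per comparison. With q = 3.6% in both arms:

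- Lost events: 0.036 × 8.3 = 0.30 and 0.036 × 14.3 = 0.51, together 0.81.
- Difference: 0.63 × (1 − 0.036) = 0.607 points.
- Power by the score formula: 80.4% becomes 82.5%.

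The 3.6% is generous. It comes from a passage on patients who have stopped treatment, and it includes deaths with a diagnosis, which count anyway.

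**3. Error at the margin.** Take true composite rates of 0.87% and 2.87%, with share q uncounted in both arms. The normal approximation gives this chance of declaring non-inferiority:

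| q (assumed) | 0 | 1% | 2% | 3.6% | 5% | 10% |
|---|---|---|---|---|---|---|
| chance | 5.0% | 5.3% | 5.7% | 6.3% | 7.0% | 9.6% |

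These count as inflation only if the composite is the quantity to be protected. Protocol 7.2 states the margin for recurrent VTE. Against that endpoint, leaving out unconfirmed deaths omits nothing, and the nominal 5% is not disturbed.

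The direction is also not fixed. At the planning rates the difference shrinks only while the warfarin share is below 0.015 / 0.0087 = 1.72 times the DOAC share (0.0287 / 0.0087 = 3.30 times at the margin).

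**4. Deaths from other causes.** With constant hazards λ1 (VTE) and λ2 (other death), the cumulative incidence is λ1/(λ1 + λ2) × [1 − exp(−λ1 − λ2)]. Censoring at death gives a difference of 0.630 points. Treating death as a competing event gives:

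| assumed mortality | 1% | 2% | 5% |
|---|---|---|---|
| difference (points) | 0.627 | 0.624 | 0.614 |

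The largest change is 0.016 points against a 2-point margin.

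**5. Would adopting the composite be neutral?** Not necessarily. The 1.5% equals the mean of 1.3% and 1.7%, although neither document gives that derivation. If that is its origin, it mixes a rate without VTE-related death and a rate with it. If counting such deaths added an assumed 0.1 to 0.5 points to both arms, power by the score formula would fall from 80.4% to between 78.1% and 70.1%.

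**The case for a change.** The strongest case for a change is that a primary endpoint should not depend on inference. The sentence that sends definitions to the charter covers only the endpoints in Protocol 2.6. A charter can classify a death as VTE-related without saying whether it enters the primary endpoint, and it would not normally set a Kaplan-Meier rule. With so few events, single cases carry weight: one extra expected DOAC event, with none on warfarin, lowers power from 80.4% to 73.2%. Writing the rule down would cost a few sentences.

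Part of this stands. The definition is silent, and a sentence settling it would do no harm. But the claim that two analysts would differ gives them a task they do not have. They take events from the blinded committee's database, and Protocol 11.9 places recurrent VTE and deaths under the same adjudication guidelines. The charter was not available, so it cannot be said that the matter is open. The contrary hint is weak as well: the phrase in the missing-data allowance makes sense without any composite, because a diagnosed fatal embolism is already an event. The Table 1 labels describe other trials' outcomes. The one-event figure assumes a loss in one arm only, and nothing in the documents points to that.

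**Conclusion.** This is a gap in wording that blinded adjudication can be expected to fill sensibly. Following the plan as written is not shown to give a wrong answer. At an assumed uncounted share of 3.6%, fewer than one event per comparison is affected and the difference moves by about 0.02 points. The choice between censoring and competing risks moves it by at most 0.016 points at assumed mortality up to 5%. No error inflation arises against the endpoint for which the margin is set. Preferring the composite to the literal reading would be a choice of estimand, not a correction, and the stated 80% power could not be carried over to it without checking the rates.

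The conclusion rests on two assumptions: that VTE deaths without a diagnosis are a small share of events, and that the committee applies one rule to all arms. A share near 10%, for which the documents give no basis, would make the choice of definition matter more. The endpoint as written would still be a legitimate one.
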